C.5. SETTING & SAMPLE. Six Head Start centers (≥ 4 classes/center) will be randomly selected from the Capital Area Community Services (CACs) Head Start and Early Childhood Programs and the Head Start for Kent County, which had 13 centers with ≥ 4 classes in 2017.^{126,127} Among the 13 centers, two had 4, one had 5, five had 6, one had 8, one had 9, two had 12, and one had 14 classes. The 13 centers cared for 1,932 preschoolers: 49% female, 20% Hispanic, 38% Black, and 39% White. Four classes will be randomly selected from each center, and 6 caregiver-preschooler dyads will be randomly selected from the eligible participants in each class (total: 6 centers, 24 classes, and 144 dyads). Inclusion and exclusion criteria are specified in **Table 1**.

C.6. SAMPLE SIZE & POWER. Due to the exploratory/developmental focus of this R21 grant proposal, our aim is to estimate effect sizes for proximal and distal outcomes in preschoolers to serve as foundation for future research. Assuming class cluster effects intraclass correlation (ICC)=0.01,^{128,129} and

significance level=.05, a sample size of 130 will provide a power of .80 to identify an effect size of 0.50, < 0.66 for MVPA achieved in the prior study after adjusting for demographics.³⁸ Given the extended intervention duration from 10 to 16 weeks and the strengthened intervention, we anticipate to also achieve an effect size of 0.50 in preschoolers' diet quality, screen time, and BMI z-score. We conservatively assume a 10% dropout.

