C.7. RECRUITMENT. The two Head Start organizations have agreed to support implementing the proposed project in their Head Start centers (**Support Letters**). Based on our prior experiences working with Head Start families, we anticipate ≥ 6 of 18 (30%) dyads per class will be willing to participate. Replacement classes will be randomly chosen if a selected class teacher refuses to participate. Building on lessons learned from prior studies and recommendations from Head Start administrators, we will involve Head Start family advocates to help with recruitment because they already have an established, trusting relationship with each family. The PI and project manager (PM) will provide participant recruitment training with communication scripts to family advocates to ensure consistency. Family advocates will distribute the recruitment packet (including cover letter, parental consent/child assent, & screening tool) in an envelope and explain the study to each caregiver in person. Each family will be asked to return the packet in a sealed envelope to the family advocate. For non-respondents, the family advocates will make a follow-up phone call, and then another packet will be mailed to each family. Each family will be asked to return the packet in an attached, prepaid envelope. Cash (\$5) will be provided for returning the packet. Prior to any data collection, written parental consent is required; if the child is age 5, written child assent is required. No data will be collected from preschoolers in the selected classes who do not have written consent or assent, but these preschoolers will be allowed to participate in intervention activities at their Head Start center. Both male and female preschoolers and caregivers will be recruited.

C.8. RANDOMIZATION AND BLINDING. Following baseline data collection, 6 randomly selected centers will be randomly assigned to intervention or control using a computerized random-number generator. Center directors and teachers will be informed of group assignment. There is no way to completely blind participants

Table 1. Inclusion and Exclusion Criteria

Preschoolers	Caregivers
Inclusion Criteria	
Parental written consent	Provide written consent
Understand and speak English	Read, understand, and speak English
3-5 years old	Primary adult caregiver (≥ 18 years old)
Enrolled in full-day or half-day Head Start program	Have at least weekly Internet access using a smartphone, tablet, or a computer

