on previous literature^{10,11,132} and our prior study. To address the unique needs of this low-SES population,⁴ the program will **1)** provide caregivers a weekly electronically retrievable flyer containing health information, family fun activities, and behavioral change strategies to help create a healthier home environment, and **2)** encourage interactive positive communication to promote peer support. All program materials will be sensitive to

participants' literacy level, low-SES & use of images as confirmed in our prior work. The program has 6 components (Table 3).

Three face-to-face caregiver meetings: MSU Extension health educators will lead the meetings at Head Start centers (wks. 1, 8, & 16; **Support Letter**) to connect caregivers to each other, offer health information, and discuss behavioral change strategies. To improve attendance and accommodate caregivers' work schedules, each meeting will be held on a weekday and a weekend day at each center. Healthy food

taste-testing activities will be offered to expose caregivers to a variety of healthy homemade meals provided by MSU Extension. **Meeting 1:** A healthy, slow cooking demonstration will be offered, and each family will receive a small bag of groceries to facilitate preparation of the demonstrated recipe at home. Alternative cooking ingredients will be discussed to help reduce sugar and fat. Each caregiver will also receive an intervention cookbook containing affordable, slow-cooking recipes, quick-fix recipes, and healthy snack ideas. Reasons for providing a cookbook are: **1)** in our prior study, Head Start caregivers requested "quick fix," affordable but healthy, recipes;⁴ and **2)** using a slow cooker to prepare easy but healthy meals is an effective strategy to overcome low-SES parent barriers of lack of time and cooking skills.^{4,133} **Meeting 2:** Extension health educators will demonstrate how to spend less and shop healthy, and how to read nutrition fact labels to promote healthy purchasing behaviors. Each caregiver will receive two, durable plastic "MyPlate" adult and child meal-portion plates to guide their proper portion size. **Meeting 3:** Extension health educators will present community healthy eating and PA resources (e.g., farmer's markets, community gardens, nearby parks or

Table 2. Caregiver Weekly Habit-Formation Tasks via Facebook

Task	Instructions

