C.13. INTERVENTION FIDELITY MONITORING & EVALUATION. The PM will monitor the Facebook group daily to record task-completion rates and caregivers' site visits, respond to caregivers' questions and postings, and review records and posted content to ensure proper posting and functionality. Extension health educators will record caregiver meeting attendance and activities, as well as each preschooler's attendance, punctuality, participation, and activities offered for the day in a daily activity log. The PI will communicate with Extension health educators weekly to review objectives, attendance, and intervention delivery dose, and discuss issues and solutions. Head Start teachers will complete an evaluation survey on preschooler program, and caregivers will complete an evaluation survey on caregiver program and preschooler letters (**Appendix A**). Two process evaluators will observe 6 randomly sampled sessions (2/center; 1 session from Extension health educator and 1 session from teacher) to evaluate preschooler curriculum implementation and activity engagement. At post-intervention, individual interviews (**Appendix A**) with 10 randomly selected caregivers will be conducted with the PM and PI to obtain in-depth evaluation of the intervention and future suggestions for improvement.

C.14. DATA COLLECTION & OUTCOME MEASURES (Table 5, Appendix A). All outcomes will be assessed at baseline and post-intervention. Height and weight will be measured in a private room in Head Start centers. To improve compliance with wearing accelerometers, an auto text-message reminder will be sent to caregivers every morning at 7AM via the *REDCap* web application maintained by MSU CTSI-BRIC (**Support Letter**). The 24-hour dietary recall will be administered by 4 trained interviewers via telephone¹⁴⁰ on 2 weekdays and 1 weekend day,^{141,142} using the Nutrition Data System for Research (NDSR) software developed by the Nutrition Coordinating Center,¹⁴³ University of Minnesota. Trained interviewers will also observe the snacks and lunch offered at Head Start centers. Drs. [name] & [name], who have completed the 2-day training on NDSR, will assess and assure diet data quality. The Environment and Policy Evaluation and Observation-Self-Report (EPAO-SR)¹⁴⁴ will be completed by each center supervisor and two teachers on a single day to assess each

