Head Start center environment, including the physical environment, provisions, practices, policies, training, and education. All other surveys will be completed by caregivers online via REDCap web application. Caregivers will be informed of online surveys via text-message or email. Data collectors and interviewers (blinded to group assignment) will be available by phone or in-person to answer questions.

Table 5. Study Measures

Concept	Measure and Description	# Items	Time	Reliability/Validity
Preschoolers (Aim 1)				
MVPA (min/day)	7-day ActiGraph GT3X-plus accelerometer ¹⁴⁵ Cut-points: sedentary activity (<37 counts/15 s), light (38–419), moderate (420–841), & vigorous (≥842) ^{146,147}	7-day	5 min	Reliability = 0.69–0.84 ¹⁴⁸ $r = 0.66$ with observational system ¹⁴⁵
Diet quality (e.g., fruit/vegetable, fiber, sugar/fat)	Intake at Head Start center: dietary observation system on snacks and lunch on two weekdays ¹⁴⁹ Intake at home: proxy-reported 24-hour dietary recall	3-day	90 min	ICC = 0.99; ¹⁴⁹ accurate rate: 95%; ¹⁵⁰ good agreement with actual energy intake ¹⁵¹
Screen Time	NHANES-Physical Activity and Physical Fitness survey ¹⁵²	2	1 min	Reliability: $r = 0.63–0.84$ ¹⁵³
Proportion of OW/O, BMI z-score	Calculated from height and weight using CDC growth charts ¹⁵⁴ Height: Child/Adult Shorr Measuring Board Stadiometer Weight: Child/Adult Seca model 874 portable electronic scale In accordance with NHANES measurement protocol ¹⁵⁵	N/A	3 min	Specificity 0.93; sensitivity 0.73 ¹⁵⁶
Caregivers (Aim 2)				
MVPA	7-day ActiGraph GT3X-plus accelerometer Cut-points: light (0–2689 counts/60 s), moderate (2690–6166), & vigorous (≥6167) ¹⁵⁷	7-day	5 min	ICC = 0.97–0.99 ¹⁵⁸ $r = 0.81$ with oxygen consumption ¹⁵⁹
Diet quality	Fruit-vegetable-fiber screener ¹⁶⁰	10	3 min	$r = 0.71$ with full Block survey ¹⁶⁰
Screen Time	NHANES-Physical Activity and Physical Fitness survey ¹⁵²	2	1 min	Reliability: $r = 0.63–0.84$ ¹⁵³
Proportion of OW/O, BMI	Calculated using (weight kg/height m^2) ¹⁶¹ Measures are similar to those used in preschoolers	N/A	3 min	Specificity 0.97; sensitivity 0.42 ¹⁶²
Knowledge	Knowledge on preschoolers' dietary intake & physical activity ¹⁶³	25	5 min	N/A
Feeding Practice Skill	Child Feeding Questionnaire ¹⁶⁴ measuring caregiver feeding practice behaviors	33	5 min	$\alpha = 0.71–0.93$ ^{38,164,165} $r = -0.26–0.53$ with child BMI ^{164–166}
Self-Efficacy	Parental self-efficacy scale ¹⁶³	20	4 min	$\alpha = 0.72–0.94$ ^{38,163}

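### Preschooler diet quality draws on observed center intake and caregiver-reported home intake with no analysis by source, so a diet effect could partly reflect a shift in reporting

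*Combined protocol and SAP*

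**What the plan says.** Table 5 gives preschooler diet quality a single row with a 3-day time base and two labelled sources. One is "Intake at Head Start center: dietary observation system on snacks and lunch on two weekdays"; the other is "Intake at home: proxy-reported 24-hour dietary recall". Section C.14 has trained interviewers take the recalls by telephone on two weekdays and one weekend day. It adds: "Trained interviewers will also observe the snacks and lunch offered at Head Start centers".

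On blinding, C.8 says of the caregivers and children that "There is no way to completely blind participants" to group. Data collectors and interviewers are blinded, caregivers are not told the hypothesis, and centers are randomized after baseline data collection.

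During the 16 weeks, intervention caregivers post about healthy meals they made and take quizzes (Table 2), learn about food labels and receive portion plates (C.10.1, Meeting 2), and report weekly which foods in the child's letter they provided (C.10.2). Control caregivers receive supplies and a session on labels and portions only after the post-intervention measurement (C.11).

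C.15 specifies mixed models with a group-by-time term, Holm's method and Cohen's d. It gives no rule for putting the two diet sources together and no analysis by source. Its only sensitivity analysis concerns missing data.

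**The concern.** The two sources carry different errors. Center intake is seen directly by staff. Home intake is what the caregiver says, and by week 17 caregivers in one arm have had months of teaching about food and practice in telling the study team what they served. Reports in that arm may change even if the child's diet does not.

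Baseline recall precedes randomization, so a shift of this kind would appear only at the post-intervention visit and only in one arm. That is the pattern the group-by-time contrast estimates. An effect on the outcome as a whole therefore cannot be attributed to diet alone.

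This matters beyond the present trial. C.6 says the effect sizes are to be a foundation for later research, and it anticipates 0.50 for diet quality.

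**Working it through.** **1. The plan's own figure.** C.6 states: "significance level=.05, a sample size of 130 will provide a power of .80 to identify an effect size of 0.50". It is used here only to obtain a standard error. Sidedness is not stated; two-sided is assumed.

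- Without clustering, d = 0.50, alpha 0.05 and power 0.80 need 63 per arm, 126 in total.
- Class size after dropout is 130/24 = 5.42. With the plan's class ICC of 0.01, the design effect is 1 + 4.42 × 0.01 = 1.044, so N = 126 × 1.044 = 131.6.
- Power at 130 is 0.797. The figure reproduces.
- Standard error of d: √(1.044 × 2/65) = 0.179.

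**2. Share of the outcome that rests on caregiver report.** The documents do not give this. Assume five eating occasions a day with equal weight, and lunch plus one or two snacks at the center on 2 of the 3 days.

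- Center: (1 + 1) × 2 = 4, or (1 + 2) × 2 = 6, of 15 occasions, which is 27% or 40%.
- Home: 73% or 60%.

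A different assumption, that the center supplies a fraction f = 0.25 to 0.50 of weekday intake, gives a home share of 1 − 2f/3 = 83% to 67% with equal days, or 1 − 5f/7 = 82% to 64% with 5:2 weekday-to-weekend weights. Table 1 admits half-day enrollees, for whom the home share may be higher. On either basis most of the outcome is caregiver-reported.

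**3. Effect of a reporting shift with no change in diet.** The shift in d is (relative shift × home share) / CV of the 3-day total. The CV is assumed to be 0.40 to 0.50, with 0.80 as a wider case. Home shares are those of the 15-occasion count.

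| Shift in reported home intake | Lowest d | Highest d |
|---|---|---|
| 10%, CV 0.40–0.50 | 0.10 × 0.60/0.50 = 0.12 | 0.10 × 0.733/0.40 = 0.18 |
| 20%, CV 0.40–0.50 | 0.24 | 0.37 |
| 10%, CV 0.80 | 0.10 × 0.60/0.80 = 0.08 | 0.10 × 0.733/0.80 = 0.09 |

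Turned round, the shift needed to produce the prior study's fruit/vegetable effect of 0.40 (C.2) by reporting alone is 0.40 × 0.40/0.733 = 22% to 0.40 × 0.50/0.60 = 33%. With the largest home share in step 2 it is 0.40 × 0.40/0.833 = 19%.

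**4. Chance of a nominally significant diet result with no change in diet** (standard error 0.179, two-sided 0.05, before Holm): 5% with no shift, 8.6% at 0.1 SD, 20% at 0.2 SD and 39% at 0.3 SD. For d = 0.12 to 0.18 it is about 10% to 17%.

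**5. The two descriptions of center data.** C.14 speaks of food offered; Table 5 speaks of intake. If only offered food were recorded, the center part would describe the menu and could not show an effect of the taste-testing sessions in Table 4. Neither place says that the observed weekdays are the recalled weekdays.

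**The case against.** The plan has real safeguards. Interviewers are blinded, caregivers are not told the hypothesis, baseline precedes randomization, and trained investigators review diet data quality (C.14). The study is exploratory and diet is not its primary outcome. These points limit the weight of the concern. They do not remove it, because blinding the interviewer does not blind the person answering.

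Several stronger readings are tempting, and the documents do not support them.

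- A reader might infer that center intake is the only diet measure recorded by blinded staff. Blinded interviewers also take the home recall; what differs is the informant.
- A reader might infer that the center data can confirm or refute the home result. The two sources cover different eating occasions, and much of the intervention is aimed at the home. A home-only effect is to be expected under true change and under a reporting shift alike, and a null center result contradicts neither.
- A reader might infer that the center observers record only the menu. The wording conflicts, but Table 5 and the title of the method it cites for observation (reference 149) both point to food intake. The phrase in C.14 may simply name the meals watched.
- A reader might infer that the sources are pooled by a fixed formula. One row suggests a combined outcome, but no rule is stated.

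The direction of any shift is also uncertain: teaching on labels and portions could make reports more accurate or lower the reported amounts.

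**Conclusion.** The point holds as a gap in the analysis of a secondary outcome. As planned, a diet effect could partly reflect a shift in caregiver reporting, and nothing in C.15 would show whether it also appears in the component that does not depend on caregiver report. Analysis by source would locate an effect; it would not settle its cause.

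The size is not known from the documents. It rests on assumed eating occasions, equal weights, assumed CVs and an assumed shift. On those terms a 10% shift is worth about d = 0.12 to 0.18, or 0.08 to 0.09 if the CV is 0.80. That a positive diet result would come wholly from reporting is a further inference that is not shown: reaching 0.40 would take a shift of roughly a fifth to a third.

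MVPA by accelerometer, the primary outcome, and the sample size are unaffected.

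**What to change.** Keep the combined diet outcome as planned, and state how the two sources are put together. Then:

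- In C.15, for each main diet component, add the same mixed model fitted separately to center-observed and to home-reported intake. Present these as supportive estimates with confidence intervals, outside the Holm family.
- State in advance that an effect seen only in home-reported intake will be described as caregiver-reported.
- Reconcile C.14 with Table 5 so that it is clear that each study child's consumption at the center is recorded.
- State that the two weekday recalls cover the same dates as the two center observations, so that each weekday forms one real 24-hour record.

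**Cost.** There are two extra fits per component. Aim 1 names at least seven components, so covering all of them would mean 14 or more; naming a few main ones keeps this small. Each source is less precise than the total, and call dates become less flexible. If consumption is already observed, the C.14 change is only wording. If it is not, staff must observe each of the 144 children on two weekdays at both time points, which is a real addition to the work.

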Our **primary objective** is to determine the preliminary efficacy of the intervention. **Methods:** We will conduct a **two-group cluster randomized controlled trial** (RCT). From the available 13 large Head Start centers, six centers will be randomly selected and then randomly assigned to the intervention (n=3) or control group (n=3, usual Head Start activities); 24 caregiver-preschooler dyads will be recruited from each center (N=144 dyads).

AIM 1: Determine the preliminary efficacy of *FirstStep2Health* vs control among preschoolers on proximal behavioral changes of ↑ moderate-to-vigorous PA (MVPA) measured by accelerometry (primary outcome), ↑ diet quality (e.g., ↑ fruits/vegetables, ↑ fiber, ↑ whole grains, ↑ total protein, ↑ dairy, ↓ sugar-sweetened beverages, ↓ total sugars/fats), and ↓ screen time (e.g., watching TV, playing video games); and distal anthropometric outcomes of ↓ proportion of OW/O and ↓ body mass index (BMI) z-score. We anticipate an overall decrease in BMI z-score in intervention preschoolers because we expect OW/O preschoolers’ BMI z-score to decrease and healthy-weight preschoolers to have no change. We focus on proximal behavioral changes as our primary outcome instead of distal anthropometric outcomes due to the brevity of this study and the need for behavioral changes to be maintained for at least a year before manifesting in changes in anthropometric outcomes.^{49,50} **AIM 2: Examine the preliminary efficacy of *FirstStep2Health* vs control among caregivers** on their ↑ MVPA measured by accelerometry, ↑ diet quality (e.g., ↑fruits/vegetables, ↑fiber), ↓ screen time, ↓ proportion of OW/O, ↓ BMI, ↑ knowledge, ↑ feeding practice skill, ↑ self-efficacy, ↑ parental support of their child, ↑ parenting practices, and ↑ home environment. **AIM 3: Compare *FirstStep2Health* vs control on the bidirectional relationship** (as demonstrated in the APIM) between preschoolers and caregivers on MVPA, diet quality, and screen time. Further, we will **validate established feasibility, acceptability, and satisfaction of the intervention using qualitative and quantitative data**.

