Parental Support	Parental support scale for eating habits and physical activity ¹⁶⁷	12	3 min	$\alpha = 0.83–0.87$ ^{38,167,168}
Parenting Practices	Parenting Style and Dimensions Questionnaire ¹⁶⁹ assessing parenting styles: authoritative, authoritarian, and permissive	32	5 min	$\alpha = 0.64–0.91$ ¹⁷⁰
Home Environment	Family Nutrition and Physical Activity (FNPA) screening tool ¹⁷¹ assessing home obesogenic environments and practices	20	4 min	Correlated with child BMI ^{171,172}
Demographics	Socio-demographic questionnaire (e.g., age, sex, race)	12	3 min	N/A
Center Environment	EPAO-SR ¹⁴⁴	1-day	30 min	Related to observational data ¹⁴⁴

C.15. DATA ANALYSIS. Any missing at random (MAR) data will be imputed using procedures suggested by Potthoff.¹⁷³ For non-MAR data, a sensitivity analysis will be performed following recommended approaches for continuous and discrete outcomes.^{174–177} All analyses will use the intention-to-treat¹⁷⁸ principle. Data analysis will be disaggregated by sex in preschoolers. **AIM 1 & 2:** Mixed-effect models in SAS 9.4 will be used to evaluate the intervention efficacy. Fixed effect predictors will include group, time, groupXtime interaction, and potential confounders such as preschooler sex, race, baseline weight status, and caregiver marital status. The correlation of preschooler outcomes measured over time and dependence due to nesting in the same center or class will be accounted through center- and class-specific random cluster effect. Contrasts will quantify the intervention effects separately at the post-intervention. Holm's method will be used to statistically control for multiple comparisons.¹⁷⁹ Effect size (Cohen's d) will be calculated. **AIM 3:** Path analysis will be conducted using EQS 6.2. Model fit will be assessed using root mean square error approximation, Normed Fit Index, and Tucker Lewis index. Chi-square difference test¹⁸⁰ will be used to compare models. Model modification will be made if needed. Feasibility/acceptability/satisfaction will be determined through enrollment, intervention participation, and evaluation survey data. Recorded individual interviews will be analyzed using directed content analysis in ATLAS.ti 8 to evaluate reasons for satisfaction and suggestions for improvement.

Table 6. Method Considerations

Issue	Justification and Strategies

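### Section C.15 does not exempt preschooler OW/O from its shared repeated-measures model; with a logit link and baseline weight status kept, the OW/O odds ratio is exaggerated and its model-based standard error too small

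*Combined protocol and SAP*

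**What the plan says.** Section C.15 describes a single mixed-effects specification for Aims 1 and 2: "Fixed effect predictors will include group, time, groupXtime interaction, and potential confounders such as preschooler sex, race, baseline weight status, and caregiver marital status". The effect is read off at week 17: "Contrasts will quantify the intervention effects separately at the post-intervention". Correlation over time and nesting "will be accounted through center- and class-specific random cluster effect"; no child-level term is named. C.15 states no link function, no separate model for a binary outcome, no coding of weight status and no reference distribution for the tests.

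Section C.14 makes the baseline value a response: "All outcomes will be assessed at baseline and post-intervention". Proportion of OW/O is a named distal outcome of Aim 1. Table 5 says how OW/O and BMI z-score are obtained: "Calculated from height and weight using CDC growth charts". The Specific Aims contrast OW/O children with healthy-weight children, expecting "healthy-weight preschoolers to have no change" in the latter.

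**The concern.** In a group, time, group-by-time model the baseline measurement is one of the two responses per child. Weight status coded as OW/O versus healthy weight, or more finely, fixes that response exactly when the outcome is OW/O. One coefficient must then serve two jobs: perfect prediction at baseline and imperfect prediction at week 17. On the logit scale it settles at a value too large for week 17, and the week-17 group contrast is estimated conditional on that wrong value.

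Section C.6 gives the aim as estimating effect sizes for proximal and distal outcomes as groundwork for later research. An exaggerated effect with too small a standard error is poor groundwork, and its p-value would enter the Holm procedure too small.

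**Working it through.** **Inputs from the documents.** N = 130 analysed, so 65 per arm, 6 centers and 24 classes (C.5, C.6, C.8); OW/O prevalence 46% in the prior study (A.1). The stated N reproduces: 63 per arm for d = 0.50, 80% power, two-sided 0.05; design effect 1 + (130/24 − 1) × 0.01 = 1.044; 126 × 1.044 ≈ 131.6; power at 130 is 0.797. This concern does not touch it.

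**Assumed.** The documents give no transition rates. I use incidence/remission of 8/12%, with 5/8% and 15/20% as the range.

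**Equations.** Let q be baseline prevalence, c the shared coefficient of baseline status, and α the intercept of each group-by-time cell. In large samples the fit satisfies:
- baseline cells: (1 − q)·expit(α0) + q·expit(α0 + c) = q
- week-17 cells: (1 − q)·expit(α1) + q·expit(α1 + c) = observed week-17 prevalence
- for c: the sum over arms of q[1 − expit(α0 + c)] + q[P11 − expit(α1 + c)] = 0, where P11 is the probability that an OW/O child is still OW/O at week 17.

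**1. Real effect, balanced arms (46%/46%), true conditional OR 0.50.**
- Control: P01 = 0.08, P11 = 0.88, so week-17 prevalence is 0.54 × 0.08 + 0.46 × 0.88 = 0.448.
- Intervention: P01 = 0.0417, P11 = 0.7857, giving 0.384.
- The correct coefficient is logit(0.88) − logit(0.08) = 4.43. The shared fit gives c = 6.16.
- Check on c: baseline residuals 2 × (1 − 0.952) = 0.096; week-17 residuals (0.88 − 0.938) + (0.786 − 0.823) ≈ −0.095. They cancel, apart from rounding.
- Week-17 intercepts are −3.448 (control) and −4.622 (intervention). The difference is −1.174, so the fitted OR is 0.31.
- The other two rate pairs also give 0.31. A true OR of 0.70 becomes 0.53.
- In simulated trials at OR 0.50, the mean log-OR was −1.25, against −0.74 for a logistic model of week-17 OW/O on group and baseline OW/O; the truth is −0.69.

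**2. No effect, baseline 40% control and 52% intervention.**
- Week-17 prevalence is 0.400 and 0.496; c = 5.96 (6.88 at 5/8%, 4.73 at 15/20%).
- Intercepts are −3.192 and −3.442, so OR = exp(−0.250) = 0.78 (range 0.77 to 0.79). The week-17 model gives 1.00.
- With the imbalance reversed the OR is 1.28, so in this null case the shift averages zero over randomisations.
- The SD of a chance imbalance is √(2 × 0.46 × 0.54/65) = 8.7 points, so the median absolute imbalance is about 0.67 × 8.7 ≈ 6 points. There the OR is 0.88 or 1.13.

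**3. Standard error, no effect, 65 per arm.**
- Shared model: true SD about 1.22, mean model-based SE 0.86; 0.86/1.22 = 0.70.
- Week-17 model: 0.67 and 0.64.
- Null rejection with z tests: about 12 to 14% against about 3%. Across the transition rates and prevalences tried (34% and 46%) it was 10 to 15% against 1.5 to 5%. With center and class intercepts fitted it was 12.0% against 2.5%.
- A 4-df t test or a child-clustered SE brings the shared model to about 2%. Neither changes the point estimate.
- In four single-dataset fits, a child random intercept had estimated variance near zero and left the contrast unchanged.

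**The case against.** **The plan may never fit this model.** The covariates are introduced as examples, no link is given, and an analyst could drop weight status when OW/O is the outcome. This stands, and it makes the point conditional. With an identity link the null shift is only 0.8 to 2.1 percentage points at a 12-point imbalance. But weight status is named, no outcome is exempted, and logit is the natural link for a binary outcome.

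**A suitable reference distribution cures the tests.** True for the excess rejection, not for the estimate; C.15 specifies neither remedy.

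**The outcome is distal.** The Specific Aims say: "We focus on proximal behavioral changes as our primary outcome instead of distal anthropometric outcomes". This stands and keeps priority low.

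**The replacement is not always better.** This stands too. If the whole 40%/52% difference is a persistent center-level difference in weight, the shared model gives 1.29 and the week-17 model 1.31 under no effect (assumed correlation over time 0.95). The plan's "Assuming class cluster effects intraclass correlation (ICC)=0.01" supports a mainly individual-level imbalance only if that figure, set for class effects in a power case on MVPA, also applies to weight.

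A reader might also infer three things that are not supported:
- That the distortion is harmless noise averaging zero. That holds only with no effect; a real effect is exaggerated even with balanced arms.
- That the missing child-level term is the cause. The child-intercept fits do not bear this out.
- That the OW/O odds ratio will be carried into the next trial. C.15 mentions no odds ratio; it names Cohen's d and does not say how that would be obtained for a binary outcome.

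**Conclusion.** The concern holds conditionally. Followed literally with a logit link and the covariate kept, C.15 predicts the baseline OW/O response from itself. At 65 per arm and 46% baseline OW/O, a true OR of 0.50 becomes about 0.31 and 0.70 about 0.53; a null OR becomes about 0.78 at 40% versus 52%; and the model-based SE is about 30% too small. The sizes rest on assumed transition rates; the exaggeration of a real effect had the same direction in every case tried.

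It would be too strong to say that the trial's main result is at risk or that the plan commits to a defective analysis. Weight status is not the baseline value of MVPA, diet quality or screen time, so those analyses are unaffected. Caregiver OW/O is affected only if weight status means the caregiver's own, which C.15 leaves unclear. Priority is low: a named secondary outcome, imprecise under either model, but with a cheap correction.

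**What to change.** Add one sentence to C.15: preschooler OW/O will be analysed with a logistic mixed model of week-17 OW/O on group, baseline OW/O status (or baseline BMI z-score) and the other covariates, with center and class random effects, and baseline rows will not be used as responses. Keep the planned model and covariate for MVPA, diet quality and screen time.

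This uses data already collected. The downsides should be stated:
- The effect is conditional on baseline status, and the model form differs from that of the other outcomes.
- Few children change status: 130 × (0.54 × 0.08 + 0.46 × 0.12) ≈ 13, or about 6 per sex. C.15 also plans analysis by sex. At 32 per arm, without covariates or random effects, about 13% of fits separated or failed, so a penalised fit or a reduced covariate set may be needed.
- Bias from large persistent center differences is not removed. Using baseline BMI z-score instead of status reduces it (1.31 to 1.09 in the case above).

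Dropping weight status for this outcome is simpler and also removes the distortion, but the week-17 OR is then unadjusted for baseline: (0.496/0.504)/(0.400/0.600) = 1.48 in the 40%/52% null case.
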